6.6 Subgroup analysis

The following subgroup variables based on baseline demographics are planned according to the subgroup analysis:

- Region (Northern America, Eastern Europe, Western Europe)
- Sex (male, female)
- Age (< Median, \geq Median)
- Weight (< Median, \geq Median)
- BMI (Underweight (<18.5), Normal (\geq 18.5 & <25), Overweight (\geq 25 & <30), Obese (\geq 30)

- Valve type (balloon-expandable, self-expandable)
- Valve-in-valve procedure
- Surgical Risk Scores:
 - Society of Thoracic Surgeons' (STS) risk score (Low (STS<3), Intermediate (3<=STS<=8), High (STS>8))
 - EuroSCORE II (low risk (<5 %), intermediate risk ($\geq 5\% & \leq 10\%$), high risk ($>10\%$))
- Renal function (Estimated Glomerular Filtration Rate):
 - $<30 \text{ mL/min/1.73 m}^2$
 - $\geq 30 \text{ & } <50 \text{ mL/min/1.73 m}^2$
 - $\geq 50 \text{ & } <80 \text{ mL/min/1.73 m}^2$
 - $\geq 80 \text{ mL/min/1.73 m}^2$
- Hypertension (yes, no)
- Diabetes mellitus (yes, no)
- History of a prior stroke (ischemic or unknown type) or non-CNS systemic embolism (yes, no)
- Prior MI (yes, no)
- Previous revascularization (CABG or PCI)
- CHADS₂ and CHA₂DS₂-VASc scores (< Median, \geq Median)
- HAS-BLED (< Median, \geq Median)
- TAVR done because of subjects frailty (yes/no)

6.6.1 Analysis of the subgroups

Subgroup analysis is done outside the scope of the main analysis.

Subgroups analysis for the primary efficacy and safety variables are based on the ITT data scope. The subgroup analyses are presented descriptively without formal hypotheses testing. Homogeneity of treatment effect in subgroups, both in magnitude and direction, is assessed by adding a covariate for the subgroup variable and the corresponding treatment subgroup interaction to the respective Cox proportional hazards model used in the main analysis. The following SAS code may be used (using subgroup male as example):

```
proc phreg data= work.infile;
model d2fDTE * DTE (0)=treat male treat*male;
run;
/*
where
work.infile = name of source dataset
```

```
treat      = randomization code
DTE       = death and thromboembolic event
d2fDTE    = days to first DTE (since randomization)
male     = 1 for male and 0 for female
*/
```

For subgroups the HR per subgroup is derived and the accompanying p-value for interaction. The following SAS code may be used:

```
proc phreg data=work.infile2;
where male = 1;
model d2fDTE*DTE(0) = treat /risklimits;
run;
proc phreg data=work.infile2;
where male = 0;
model d2fDTE*DTE(0) = treat /risklimits;
run;
/*
where
work.infile = name of source dataset
treat      = randomization code
DTE       = death and thromboembolic event
d2fDTE    = days to first DTE (since randomization)
male     = 1 for male and 0 for female
*/
```

The p-value for interaction can also be obtained from the first phreg statement in this section (with the interaction term).

A forest plot will be created to visualize the results.

The analysis of the subgroups are visualized in [flowchart 5](#) in appendix I.

As the number of subgroup analyses is large, the probability of observing at least one spurious interaction is high despite the lack of a biological or pharmacological basis for expecting an interaction. Thus, any interactions with a p-value below the 5% type I error level in the analysis of primary variables will be interpreted as “flags” to prompt further investigation. This further investigation may include the likelihood ratio test proposed by Gail and Simon to test for qualitative interaction.^{9,10}

[figure not shown]

7. Document history and changes in the planned statistical analysis

[figure not shown]
None.

8. Appendix I Flowcharts

[figure not shown]

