6.2. Exclusion criteria

Subjects are NOT eligible to participate in this trial if they meet ANY of the following exclusion criteria:

General

- 1. Any atrial fibrillation (AF), at the time of randomization or previous, with an ongoing indication for oral anticoagulant treatment
- 2. Any other indication for continued treatment with any oral anticoagulant (OAC)

Bleeding risks or systemic conditions

- 3. Known bleeding diathesis, such as but not limited to:
 - a. active internal bleeding, clinically significant bleeding, bleeding at a non-compressible site, or bleeding diathesis,
 - b. platelet count $\leq 50,000/\text{mm}^3$ at screening
 - c. hemoglobin level $< 8.5 \text{ g/dL}$
 - d. history of intracranial hemorrhage or subdural hematoma
 - e. major surgery, biopsy of a parenchymal organ, or serious trauma within 30 days before randomization
 - f. active peptic ulcer or known upper GI bleeding within the last 3 months

Concomitant and study medication

- 4. Any ongoing absolute indication for dual-antiplatelet therapy (DAPT) at time of screening that is unrelated to the TAVR procedure
- 5. Known hypersensitivity or contraindication to acetylsalicylic acid, clopidogrel or rivaroxaban or hypersensitivity to contrast media that could not be solved neither by switching to an alternate contrast media nor with pre-treatment with appropriate medication
- 6. Routine use of oral non-steroidal anti-inflammatory drugs (NSAID)
- 7. Concomitant therapy with systemic drugs that are strong inhibitors of both CYP 3A4 and P-gp (azole antimycotics such as ketoconazole and itraconazole or HIV protease inhibitors such as ritonavir)
- 8. Concomitant therapy with drugs that are strong CYP 3A4 inducers (e.g. carbamazepine, phenytoin, rifampin, St. John's wort)

9. Concomitant therapy with omeprazole or esomeprazole that cannot be switched to an alternate medication.

Concomitant conditions

10. Planned coronary or vascular intervention or major surgery
11. Clinically overt stroke within the last 3 months
12. Severe renal impairment (eGFR < 30 mL/min/1.73 m²) or on dialysis, or post-TAVR unresolved acute kidney injury with renal dysfunction stage 2 or higher
13. Moderate and severe hepatic impairment (Child-Pugh Class B or C) or any hepatic disease associated with coagulopathy
14. Active infective endocarditis

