10.3.5.1. Testing for superiority

This section was modified with Amendment 3. For details, see Section 15.2.

In order to evaluate whether the rivaroxaban-based strategy is superior to the antiplatelet-based strategy in prolonging the time to primary efficacy outcome event in patients with post-TAVR patients, the following null hypothesis (H_0) is tested at the significance level of 2.5%:

$H_0: S_{RIV}(t) = S_{APT}(t)$ for all time points $t \geq 0$, (i.e. “there is no difference between the rivaroxaban-based treatment group and the antiplatelet-based control group regarding the primary efficacy outcome for all time points”)

The one-sided alternative hypothesis is:

$H_1: S_{RIV}(t) > S_{APT}(t)$ for at least one time point $t \geq 0$, and $S_{RIV}(t) \geq S_{APT}(t)$ for all time points $t \geq 0$, (i.e. “there is a difference between the two groups in favor of the rivaroxaban-based treatment group regarding the primary efficacy outcome for at least one time point”)

where S_{RIV} denotes the event-free survival function of the rivaroxaban-based treatment group and S_{APT} denotes the event-free survival function of the antiplatelet-based treatment group.

The following decision rule to test the null hypothesis is applied:

According to the size of this study, it is justified to assume under H_0 a sufficiently close approximation of the one-sided log-rank test to the normal distribution. If the z-value from the one-sided log-rank test (for the difference $S_{RIV}(t) - S_{APT}(t)$) is larger than the critical quantile from the normal distribution ($z_{0.975} = 1.96$), the null hypothesis is rejected in favor of the alternative hypothesis.

Kaplan-Meier estimates of cumulative risk and cumulative hazard functions are provided to evaluate the timing of event occurrence in the different treatment groups and the consistency of the respective treatment effects for all time points.

Hazard ratio and corresponding two-sided 95% confidence intervals are estimated based on a Cox proportional hazards models. The parameter estimate β ($=\ln(HR)$), its standard error, p-value, and 95% Confidence Limits are calculated according to the maximum partial likelihood method, with Breslow's approximation for ties (phreg).

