10.4. Determination of sample size

This section was modified with Amendment 3. For details, see Section 15.2.

The sample size determination for the study was driven by requirements for testing superiority of the rivaroxaban-based strategy over the antiplatelet-based strategy as described above.

The expected 540 days event rate of the primary efficacy endpoint is 33.0% (5-7, 10). The target Relative Risk at 540 days is 0.80, i.e. a reduction of the 540 days event rate from 33.0% under antiplatelet-based regimen to 26.4% under the rivaroxaban-based regimen. Under the assumption of an exponential distribution, the hazard ratio equals 0.7654.

Under the above assumptions, with 360 days accrual period, and an 540 days median follow-up (minimum 360 days and maximum 720 days), randomization of 2 x 740 analyzable subjects is expected to yield 440 primary events (196 in the rivaroxaban-based treatment group and 244 in the antiplatelet-based control group). This provides 80% power at a 5% significance level, without interim analyses for efficacy.

The power calculation was based on a test using the Cox proportional hazards model and was performed with PASS version 12.0.6, with the module for two survival curves using Cox's proportional hazards model.

A sample size of sample size of 2 x 760 subjects allows for an attrition rate of 2.63%. The study is event driven and the number of randomized subjects is estimated to be required to collect 440 primary efficacy events. The study is planned to run until this number of events has been reached or to stop earlier if the event rate is unexpectedly low.

With this sample size, the study has > 90% power to show non-inferiority with a non-inferiority margin of 1.20 if the underlying hazard ratio ≤ 0.90 at a one-sided significance level of 2.5%. The non-inferiority margin of 1.20 was selected based on clinical appropriateness.

The final sample size will depend on multiple factors including the rate of accrual of the primary endpoint events. The Steering Committee of the trial will monitor the aggregate (blinded) event rate and may increase the sample size or duration of follow-up to achieve the planned target number of events in consultation with the sponsor.

Non-inferiority margin

The non-inferiority margin of 1.20 for the HR for the efficacy comparison as described in Section 10.3.5.2 was selected based on both clinical appropriateness and relevant studies in the area of TAVR.

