6.1.2 Demographics

The following demographic and baseline characteristics will be summarized by treatment group in FAS. Summary statistics will be presented for metric variables and frequency tables will be presented for categorical variables.

- Sex (% male)
- Age (continuous, year)
- Age (categorical <median, \geq median, \leq 75 year, $>$ 75 year, \leq 85 year, $>$ 85 year)
- Weight (continuous, kg)
- BMI (continuous, kg/m²)
- Ethnicity (categorical as specified in eCRF)
- Race (categorical as specified in eCRF)
- Current/recent smoker (<1 year) (% yes)
- Diabetes mellitus (% yes,)
- eGFR at screening (<30 ml/min/1.73m², \geq 30 to \leq 50 ml/min/1.73m², $>$ 50 to \leq 80 ml/min/1.73m², $>$ 80 ml/min/1.73m²)

Other baseline characteristics may be added.

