6.1.4 TAVR details

The following TAVR details will be summarized by treatment group in FAS. Summary statistics will be presented for metric variables and frequency tables will be presented for categorical variables as specified in [4.1](#)

- TAVR due to subjects frailty (% yes)
- EuroScore II (final) (continuous)
- STS score (final) (continuous)
- Brand name of aortic valve (categorical as specified in eCRF)
- Size of aortic valve (continuous)
- Valve in valve procedure (% yes)

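### Homogeneity of treatment effect is assessed only on median splits and bands of variables available as continuous values, and the planned eGFR <30 subgroup is one the protocol excludes

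*SAP*

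**What the plan says.** SAP 6.6 defines the subgroup variables. Age, weight, CHADS2, CHA2DS2-VASc and HAS-BLED are split at the median. STS has three bands, "Low (STS<3), Intermediate (3<=STS<=8), High (STS>8", and so has EuroSCORE II. BMI and eGFR have four bands each, and the lowest eGFR band is below 30 mL/min/1.73 m².

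SAP 6.6.1 then states how homogeneity will be judged: "assessed by adding a covariate for the subgroup variable and the corresponding treatment subgroup interaction to the respective Cox proportional hazards model". No interaction on the uncut scale is planned. The section calls the subgroup work descriptive, but it adds a rule: "any interactions with a p-value below the 5% type I error level in the analysis of primary variables will be interpreted as" flags that prompt further investigation. The rule covers both primary efficacy and primary bleeding.

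The uncut values are to hand. SAP 6.1.2 lists "Age (continuous, year") and likewise weight and BMI. SAP 6.1.4 lists "STS score (final) (continuous") and EuroSCORE II. The SAP tabulates eGFR only in bands, but Protocol 9.6.3.1 derives it from serum creatinine or takes it from the laboratory printout.

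Protocol 6.2, criterion 12, excludes "Severe renal impairment (eGFR < 30 mL/min/1.73 m²) or on dialysis".

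**The concern.** The interaction p-value is the plan's only screen for effect heterogeneity across these variables. If benefit or bleeding risk changes gradually with age, surgical risk or renal function, a cut variable treats everyone within a group as alike, and the screen is more likely to miss the gradient than it needs to be. A gradient is not far-fetched on the protocol's own account: Protocol 3.4 says that rivaroxaban concentrations differ in the elderly, mainly through reduced renal clearance.

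The lowest renal band is a second, smaller problem. A planned subgroup that eligible subjects cannot enter at screening gives a hazard ratio that is unstable or cannot be estimated.

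**Working it through.** **The plan's own figure.** Protocol 10.4 gives 540-day event rates of 33.0% and 26.4%, hazard ratio 0.7654 and 440 events: "This provides 80% power at a 5% significance level, without interim analyses for efficacy". Protocol 10.3.5.1 uses a one-sided 2.5% level, so z = 1.96.

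- HR = ln(1 − 0.264)/ln(1 − 0.33) = 0.7654.
- Events = 4(1.96 + 0.84)²/(ln 0.7654)², which gives 440 with unrounded quantiles.
- Exponential event times with uniform accrual (follow-up 360 to 720 days) give 194 + 243 = 437 events from 2 × 740 subjects, against 440 stated. With 1520 subjects the figure is 437 × 1520/1480 = 449.

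The design figures reproduce. The documents state no power for any interaction, so what follows is my calculation at 440 events.

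**Median split.** For 1:1 allocation and an interaction slope b per SD of the covariate, the variance of the estimate is about 4/440, so the mean of z is b√(440/4) = 10.49b. The share of information a grouped version keeps is its squared correlation with the continuous value. For a normal covariate cut at the median this is 2/π = 0.637.

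- Slope giving 80% power on the continuous scale: b = 2.80/10.49 = 0.267, a ratio of hazard ratios of 1.31 per SD.
- After the split: mean z = 2.80 × √0.637 = 2.23; power = Φ(2.23 − 1.96) = 61%.
- Equivalent events: 440 × 0.637 = 280.
- Check on 300 simulated Cox trials (1480 subjects, about 439 events): 79.7% continuous, 60.3% split.
- Other assumed shapes: uniform keeps 75%, left-skewed 65%, lognormal (sigma 0.5) 52%.
- Modest slope, b = 0.10: 18% continuous, 13% split.

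**Bands.** The documents give no distributions, so these are assumptions. The share kept is the part of the covariate's variance lying between bands.

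| Variable | Assumed distribution | Information lost, bands as a trend |
|---|---|---|
| BMI | normal, mean 26–29, SD 4–6 | 14–18% |
| eGFR | normal, mean 55–70, SD 18–22, <30 removed | 20–22% |
| STS | lognormal, median 3–5, log SD 0.6–0.8 | 19–27% |
| EuroSCORE II | lognormal, median 3–5, log SD 0.6–0.8 | 24–49% |

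The two surgical scores are taken as linear on the log scale. Bands are scored at their means; integer codes lose less than one percentage point more.

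If bands enter as categories, the extra degrees of freedom cost power. With b = 0.267 and equal-sized bands, three bands (79% kept, 2 df) give about 60% and four bands (86% kept, 3 df) about 57%. The SAP does not say which coding applies: its example uses a binary variable and no CLASS statement.

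**Renal band.** Under criterion 12 the expected count below 30 is zero. SAP 5.1 keeps every randomized subject in the full analysis set, and Protocol 6.3.1.1 foresees erroneous randomization, so a few subjects may appear there.

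**The case against.** The strongest reply is that little hangs on this. SAP 6.6.1 places subgroup analysis outside the main analysis and without formal testing, and its stated worry is spurious interactions, not missed ones. The 80%-versus-61% contrast also needs a steep gradient: the hazard ratio would run from 0.7654/1.306 = 0.59 at −1 SD to 0.7654 × 1.306 = 1.00 at +1 SD. For modest gradients both analyses usually miss. If the effect truly steps at the median, the order reverses (59% continuous, 80% split, by simulation). Some cuts are also anchored in the protocol: eGFR 30 is an eligibility limit and eGFR 50 a dose boundary after new-onset atrial fibrillation.

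All of that stands, and it rules out stronger readings that a reader might infer:

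- That every grouped variable loses a third of its information. That fits median splits of a roughly normal covariate; bands as a trend mostly lose less.
- That CHADS2, CHA2DS2-VASc and HAS-BLED are mishandled continuous data. They are integer scores, and Protocol 10.3.4 itself sets their median cuts, as it does for age.
- That the continuous term should replace the bands as the source of the flag. Protocol 10.3.8 prescribes the interaction on the subgroup variable, and no single functional form is best against every alternative.
- That the <30 band necessarily spends a degree of freedom. If it is empty, it does not.

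None of this explains why the continuous values should go unused in a screen for heterogeneity.

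**Conclusion.** The point holds as a cheap improvement to an exploratory screen. For age and weight, the planned split keeps about 64% of the information on a linear interaction (52–75% by shape), and power falls from 80% to about 61% at 440 events. For the banded variables the loss is mostly 14–27% as a trend (EuroSCORE II 24–49%), or a power similar to the split if they enter as categories.

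These figures rest on assumed distributions and a roughly linear interaction, neither of which the documents supply. The power figures are for the efficacy endpoint. The information shares carry over to bleeding under the same assumptions, but I computed no bleeding power.

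A reader might infer that the trial's conclusions are at risk. They are not: the superiority and non-inferiority tests do not use these models. The eGFR <30 subgroup should be empty or hold essentially only deviations, so its separate hazard ratio would tell the reader almost nothing.

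**What to change.** In SAP 6.6.1, keep the planned bands, their hazard ratios, the banded interaction p-value and the forest plot. Add a prespecified interaction of treatment with the continuous value of age, weight, BMI, STS, EuroSCORE II and eGFR: a linear term, with a spline as a check, reported beside the banded p-value. In code this is one more phreg step with the uncut variable in place of the subgroup indicator.

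In SAP 6.6, merge eGFR <30 with 30 to <50 for the subgroup hazard ratio and the interaction. This keeps the boundary at 50.

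The cost is SAP wording and a few lines of code. No data collection, sample size or primary analysis changes, and because the protocol's groupings stay, the continuous terms only add to them. The downsides are a few more exploratory p-values, possibly extra flags, and less power for the continuous term where the effect truly steps at a cut, which the retained bands would still show.

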8.1 Flowchart 1: Primary efficacy

[figure not shown]

8.2 Flowchart 2: Secondary efficacy, secondary safety and other variables

[figure not shown]

